- No decline in Eastern Cooperative Oncology Group (ECOG) performance status
- Absence of rapid progression of disease
- Absence of progressive tumor at critical anatomical sites (e.g., cord compression) requiring urgent alternative medical intervention

When feasible, subjects should not be discontinued until progression is confirmed. This allowance to continue treatment despite initial radiologic progression takes into account the

observation that some subjects can have a transient tumor flare in the first few months after the start of immunotherapy, but with subsequent disease response. Subjects that are deemed clinically unstable are not required to have repeat imaging for confirmation of progressive disease.

A retrospective central review may be performed for subjects using RECIST 1.1 criteria to assess best overall response. Response activity by RECIST 1.1 in GBM subjects may be retrospectively confirmed using central review RANO criteria [30], and similarly prostate cancer subject radiologic activity may be retrospectively confirmed using central PCWG2 criteria [31].

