5.5.1 Acceptable Concomitant Medications

All treatments that the investigator considers necessary for a subject's welfare may be administered at the discretion of the investigator in keeping with the community standards of medical care. All concomitant medication will be recorded on the electronic case report form eCRF including all prescription, over-the-counter (OTC), herbal supplements, and IV medications and fluids. If changes occur during the trial period, documentation of drug dosage, frequency, route, and date may also be included on the eCRF.

All concomitant medications received within 28 days before the first dose of trial treatment and 30 days after the last dose of trial treatment should be recorded. Concomitant medications administered after 30 days after the last dose of trial treatment should be recorded for SAEs and ECIs as defined in Section 7.2.

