5.5.2 Prohibited Concomitant Medications

Subjects are prohibited from receiving the following therapies during the Screening and Treatment Phase (including retreatment for post-complete response relapse) of this trial:

- Anti-cancer systemic chemotherapy or biological therapy

Note: Subjects with glioblastoma multiforme with any prior bevacizumab treatment are not eligible (exceptions may be considered after consultation with the sponsor).

Note: Subjects with prostate cancer who are currently on LHRH analogs and subjects with breast cancer receiving LHRH analogs for ovarian suppression to avoid menses are eligible for this study and may continue to take the LHRH analogs while participating in this study.

- Immunotherapy not specified in this protocol
- Chemotherapy not specified in this protocol
- Investigational agents other than pembrolizumab
- Radiation therapy

Note: Radiation therapy to a symptomatic solitary lesion or to the brain may be allowed after consultation with Sponsor.

- Live vaccines within 30 days prior to the first dose of trial treatment and while participating in the trial. Examples of live vaccines include, but are not limited to, the following: measles, mumps, rubella, chicken pox, yellow fever, rabies, BCG, and typhoid (oral) vaccine. Seasonal influenza vaccines for injection are generally killed virus vaccines and are allowed; however intranasal influenza vaccines (e.g. Flu-Mist®) are live attenuated vaccines, and are not allowed
- Glucocorticoids for any purpose other than to modulate symptoms from an adverse event.

Note: The use of physiologic doses (e.g., prednisone 10 mg) of corticosteroids may be approved after consultation with the Sponsor. Concomitant administration of higher steroid doses with study medication is prohibited.

Note: Systemic steroid therapy allowed for subjects in the GBM cohort as long as \leq dexamethasone 4 mg, or its steroid equivalent (other exceptions may be considered after sponsor consultation).

Note: Use of prophylactic corticosteroids to avoid allergic reactions (e.g. IV contrast dye) is permitted.

Subjects who, in the assessment by the investigator, require the use of any of the aforementioned treatments for clinical management should be removed from the trial. Subjects may receive other medications that the investigator deems to be medically necessary.

The Exclusion Criteria describes other medications which are prohibited in this trial.

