7.1.2.5.3 Tumor Imaging During Trial

Tumor imaging may be performed by CT or magnetic resonance imaging (MRI), but the same imaging technique should be used in a subject throughout the trial. Imaging should be performed every 8 weeks (56 days ± 7 days) from the first dose of trial treatment or more frequently if clinically indicated. After 6 months, imaging should be performed every 12 weeks (84 ± 7 days). Imaging timing should follow calendar days and should not be delayed for delays in cycle starts or withholding of pembrolizumab cycle intervals.

Per RECIST 1.1, PR and CR response should be confirmed by a repeat radiographic assessment not less than 4 weeks from the date the response was first documented. The tumor imaging performed for confirmation of response may be performed at the earliest 4 weeks after the first indication of response, or at the next scheduled scan, whichever is clinically indicated.

Imaging should continue to be performed until documented disease progression, the start of new anti-cancer treatment, withdrawal of consent, death, or the end of the study, whichever occurs first. Disease progression should be confirmed at least 4 weeks after the first scan indicating progressive disease in clinically stable subjects. Subjects who have unconfirmed disease progression may continue on treatment until progression is confirmed provided they have met the conditions detailed in Section 7.1.2.5.1.

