8.2.3.1 Efficacy Endpoints

Efficacy endpoints that will be evaluated for are listed below, followed by the descriptions of the derivations of selected endpoints.

The primary efficacy endpoint is best ORR, defined as the proportion of subjects in the analysis population who have CR or PR based on assessments by the investigator, and confirmed per RECIST 1.1 at any time during the study. Response for the primary analysis will be determined by the investigator assessment, and a confirmation assessment is required per RECIST 1.1.

Secondary efficacy endpoints include: (1) DOR, defined as time from first RECIST 1.1 response to disease progression in subjects who achieve a PR or better based on assessments by the investigator, and confirmed per RECIST 1.1; (2) PFS, defined as the time from allocation to the first documented disease progression based on assessments by the

investigator, and confirmed per RECIST 1.1 or death due to any cause, whichever occurs first; and (3) OS, defined as the time from first dose of trial medication to the time of death due to any cause.

Additional supportive analyses of best ORR, DOR, and PFS will be conducted using modified RECIST 1.1 criteria, in which a confirmation assessment of disease progression must be obtained at least 4 weeks after the initial disease assessment indicating progressive disease.

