12.5 Common Terminology Criteria for Adverse Events V4.0 (CTCAE)

The descriptions and grading scales found in the revised NCI Common Terminology Criteria for Adverse Events (CTCAE) version 4.0 will be utilized for adverse event reporting. (https://ctep.cancer.gov/protocolDevelopment/electronic_applications/ctc.htm).

12.6 Response Evaluation Criteria in Solid Tumors (RECIST) 1.1 Criteria For Evaluating Response in Solid Tumors

RECIST version 1.1* will be used in this study for assessment of tumor response. While either CT or MRI may be utilized, as per RECIST 1.1, CT is the preferred imaging technique in this study.

** As published in the European Journal of Cancer:*

12.7 Updated Response Assessment Criteria for High-Grade Gliomas: Response Assessment in Neuro-Oncology Working Group

RANO criteria* will be used in this study to retrospectively confirm RECIST 1.1 response activity in GBM subjects using central review. While either CT or MRI may be utilized, as per RANO criteria, MRI is the preferred imaging technique for this cohort.

** As published in the Journal of Clinical Oncology:*

12.8 Design and End Points of Clinical Trials for Patients With Progressive Prostate Cancer and Castrate Levels of Testosterone: Recommendations of the Prostate Cancer Clinical Trials Working Group

PCWG2 criteria* will be used in this study to retrospectively confirm RECIST 1.1 response activity in prostate cancer subjects using central review. The primary imaging modality for this cohort is CT for tumor assessment, with a bone scan to be considered at screening if consistent with local standard of care practices. Bone scans may be performed at subsequent time points when clinically indicated such as in the presence of new bone pain.

** As published in the Journal of Clinical Oncology:*

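### In the glioblastoma cohort (E1), steroids may be started or raised on study up to a stated ceiling, and neither the RECIST 1.1 response nor any planned sensitivity analysis takes steroid dose into account

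*Combined protocol and SAP*

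**What the plan says.** **Steroid use.** Section 5.5.2 lists among prohibited therapies "Glucocorticoids for any purpose other than to modulate symptoms from an adverse event". A note then exempts one cohort: "Systemic steroid therapy allowed for subjects in the GBM cohort as long as" the dose does not exceed "dexamethasone 4 mg, or its steroid equivalent (other exceptions may be considered after sponsor consultation". Exclusion criterion 2 in Section 5.1.3 carries the same allowance at entry. Neither place requires a stable or non-increasing dose.

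**Response.** Section 8.2.3.1 defines the primary endpoint alike for all cohorts: "Response for the primary analysis will be determined by the investigator assessment, and a confirmation assessment is required per RECIST 1.1". Section 7.1.2.5.3 sets the confirmation scan at "not less than 4 weeks from the date the response was first documented". Neither section mentions steroids, nor does the adaptation of RECIST 1.1 in Sections 4.2.3.1 and 7.1.2.5.1. Sections 8.2.5.1 and 8.2.9 let interim decisions rest on unconfirmed responses.

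**Glioma-specific review.** Section 3.3 places RANO under an exploratory objective marked optional. Section 4.2.3.1 says "Response activity by RECIST 1.1 in GBM subjects may be retrospectively confirmed using central review RANO criteria". Section 12.7 says the RANO criteria "will be used in this study to retrospectively confirm RECIST 1.1 response activity in GBM subjects using central review".

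**Recording.** Section 5.5.1 makes recording of all concomitant medication mandatory, and footnote f of the flow chart in Section 6.1 requires newly started medications to be entered. For changes during the trial, however, "documentation of drug dosage, frequency, route, and date may also be included on the eCRF".

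**The concern.** E1 is the only cohort with a standing allowance for systemic steroid therapy on study. A subject who is off steroids at the baseline scan may start them, and one on a low dose may go up to the ceiling, without breaking the protocol. If measured lesions shrink for that reason, the investigator's RECIST 1.1 reading can be PR or CR. If the higher dose continues, the confirmation scan some weeks later does not separate this from a drug effect.

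The trial has no control arm, so nothing offsets such a shift. The cohort is small and the success threshold is 6 of 22, so each extra responder adds 1/22 = 4.5 percentage points. The planned analyses would not reveal the problem: Table 14 has no steroid-related analysis, and Section 8.2.8 plans no subgroup analysis. What is at stake is how far an E1 go decision can be attributed to pembrolizumab.

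**Working it through.** **Inputs.** From Section 8.2.7: null response rate 0.10, alternative 0.35, one-sided alpha 0.08, beta 0.20, first look at 6 subjects, maximum 22, final success at 6 or more confirmed responders of 22. Monitoring bounds are from Tables 11 and 12.

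**The plan's own figures.** Exact enumeration of the bounds after every subject from 6 to 22 gives these probabilities of crossing the efficacy bound before futility:
- 0.814 at a true rate of 35% (Table 15 states 0.80)
- 0.048 at a true rate of 10% (Table 15 states 0.05)

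All nine go probabilities in Table 15 reproduce within 2 points. With stopping for futility only, average sample size is 9.9 at 10% and 20.1 at 35%, as stated. The plan's arithmetic is sound; the point concerns what is counted as a response.

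**Effect of k steroid-attributed responders, true rate 10%.** Suppose k of the 22 are scored as confirmed responders because of a steroid change, and the other 22 − k respond independently at 0.10. Without early stopping, P(success) = P(X ≥ 6 − k), with X binomial on 22 − k subjects. In the last column Table 12 is applied after each subject from the sixth, with the k subjects placed at random in the enrollment order.

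| k | Formula | No stopping | With Table 12 stopping |
|---|---|---|---|
| 0 | P(X ≥ 6), n = 22 | 0.018 | 0.015 |
| 1 | P(X ≥ 5), n = 21 | 0.052 | 0.044 |
| 2 | P(X ≥ 4), n = 20 | 0.133 | 0.112 |

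One such subject leaves the final rule below 0.08; two take it above.

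**The same question as a rate.** Let a fraction s of true non-responders be misclassified. The observed rate is then 0.10 + 0.90s.

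| s | Observed rate | P(at least 6/22), no stopping | P(efficacy bound crossed before futility) |
|---|---|---|---|
| 0 | 0.100 | 0.018 | 0.048 |
| 2% | 0.118 | 0.038 | 0.079 |
| 5% | 0.145 | 0.088 | 0.143 |
| 10% | 0.190 | 0.228 | 0.288 |

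At s = 5% the expected number misclassified is 22 × 0.90 × 0.05 = 0.99, but the actual number varies, which is why the final rule then slightly exceeds 0.08. The last column is more sensitive. It describes crossing a bound that opens future study planning and may use unconfirmed responses, not final success.

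**What is assumed.** The documents do not say that steroids alter measured lesion size, how large the effect might be within the ceiling, or how many E1 subjects raise their dose. The values of k and s are illustrations, not estimates.

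**The case against.** The strongest case against the point runs as follows.

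- **Exposure is bounded.** A reader might infer that E1 subjects may take steroids without limit. The documents do not support that. There is a ceiling at entry and on study, going above it needs a sponsor exception or an adverse-event indication, and Section 5.5.2 says subjects who need prohibited treatment should leave the trial. This stands, and it limits the size of the problem. It does not remove it, because a move from none up to the ceiling is allowed.
- **New starts are recorded.** A reader might infer that a steroid start could go unrecorded. Section 5.5.1 and footnote f rule that out. The gap is narrower: dose and date details of later changes are permissive, so the dose at each scan is not assured.
- **The mechanism is outside the documents.** This stands. The text establishes only that such shrinkage would be counted if it occurred.
- **Central RANO review may follow.** Section 7.1.2.5.1 provides for central image review that may include RANO, and Section 8.2.7 allows extra enrollment so that enough subjects are evaluable for it. This is partial mitigation at most. On every wording it is a retrospective check that leaves the primary response and the 6/22 rule unchanged, and the documents do not set out what RANO requires about steroids.
- **The aim is a preliminary signal in one of 20 cohorts.** This is fair, and it argues for a proportionate remedy.

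**Conclusion.** The point holds in a limited form. E1 alone combines a standing steroid allowance, no stable-dose condition, and a response definition that ignores steroid dose. Conditional on the stated assumption, at a true rate of 10% two or more steroid-attributed confirmed responders among 22 would take the final success probability above 0.08 (0.133, or 0.112 with futility stopping). One would not (0.052, or 0.044).

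Two stronger conclusions might be inferred and are not supported. The first is that the E1 response rate will be biased; without any documented effect size or frequency, only the possibility follows. The second is that the E1 primary endpoint has to be redefined. Table 3 directs corticosteroids for many immune-related adverse events, so a primary definition conditioned on steroid dose would score some genuine responders as failures because of the drug's own toxicity. Changing primary methods would also need a protocol amendment under Section 8.0. A sensitivity analysis meets the concern without that trade-off.

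**What to change.** Four changes, none of which alters permitted steroid use:

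1. Keep investigator RECIST 1.1 response rate as the E1 primary endpoint. Add to Section 8.2.3.1 and Table 14 a prespecified E1 sensitivity analysis in which a CR or PR counts only if the systemic steroid dose at both the response scan and the confirmation scan is no higher than at the baseline scan. Show separately the responders whose increase was for an immune-related adverse event.
2. State that any E1 go decision is read alongside that analysis.
3. In Section 5.5.1, change *may* to *will* for steroid dose and dates of change in E1.
4. Reconcile the status of the RANO review across Sections 3.3, 4.2.3.1 and 12.7, which now read as optional, permissive and definite respectively.

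The cost is some extra data entry in one cohort, one more analysis, and text in the protocol's own statistical section, since no separate SAP is issued for these endpoints. The sensitivity response rate may be lower than the primary one because true responders who needed more steroid are scored conservatively; the separate display in item 1 shows how much of any gap comes from immune-related events.

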5.6 Rescue Medications & Supportive Care

5.6.1 Supportive Care Guidelines

Subjects should receive appropriate supportive care measures as deemed necessary by the treating investigator including but not limited to the items outlined below:

- Diarrhea: Subjects should be carefully monitored for signs and symptoms of enterocolitis (such as diarrhea, abdominal pain, blood or mucus in stool, with or without fever) and of bowel perforation (such as peritoneal signs and ileus). In

symptomatic subjects, infectious etiologies should be ruled out, and if symptoms are persistent and/or severe, endoscopic evaluation should be considered.

- All subjects who experience diarrhea should be advised to drink liberal quantities of clear fluids. If sufficient oral fluid intake is not feasible, fluid and electrolytes should be substituted via IV infusion.
- Nausea/vomiting: Nausea and vomiting should be treated aggressively, and consideration should be given in subsequent cycles to the administration of prophylactic antiemetic therapy according to standard institutional practice. Subjects should be strongly encouraged to maintain liberal oral fluid intake.
- Anti-infectives: Subjects with a documented infectious complication should receive oral or IV antibiotics or other anti-infective agents as considered appropriate by the treating investigator for a given infectious condition, according to standard institutional practice.
- Immune-related adverse events: Suggested supportive care measures for the management of AEs with potential immunologic etiology are outlined along with dose modification guidelines in Section 5.2.1.2, [Table 3](#) and Section 5.6.1.1 below.
- Management of Infusion Reactions: Pembrolizumab may cause severe or life threatening infusion-reactions. Acute infusion reactions (which can include cytokine release syndrome, angioedema, or anaphylaxis) are different from allergic/hypersensitive reactions, although some of the manifestations are common to both AEs. Signs and symptoms usually develop during or shortly after drug infusion and generally resolve completely within 24 hours of completion of infusion. Signs/symptoms may include: Allergic reaction/hypersensitivity (including drug fever); Arthralgia (joint pain); Bronchospasm; Cough; Dizziness; Dyspnea (shortness of breath); Fatigue (asthenia, lethargy, malaise); Headache; Hypertension; Hypotension; Myalgia (muscle pain); Nausea; Pruritus/itching; Rash/desquamation; Rigors/chills; Sweating (diaphoresis); Tachycardia; Tumor pain (onset or exacerbation of tumor pain due to treatment); Urticaria (hives, welts, wheals); Vomiting. Dose modification and toxicity management guidelines on pembrolizumab associated infusion reaction are provided in [Table 5](#).

Table 5 Pembrolizumab Infusion Reaction Dose Modification and Treatment Guidelines

NCI CTCAE Grade	Treatment	Premedication at Subsequent Dosing

Grade 1 Mild reaction; infusion interruption not indicated; intervention not indicated
	
Increase monitoring of vital signs as medically indicated until the subject is deemed medically stable in the opinion of the investigator.
	
None


Grade 2 Requires infusion interruption but responds promptly to symptomatic treatment (e.g., antihistamines, NSAIDs, narcotics, IV fluids); prophylactic medications indicated for ≤24 hrs
	
Stop Infusion and monitor symptoms. Additional appropriate medical therapy may include but is not limited to:
 
 • IV fluids • Antihistamines • NSAIDs • Acetaminophen • Narcotics 
Increase monitoring of vital signs as medically indicated until the subject is deemed medically stable in the opinion of the investigator. If symptoms resolve within 1 hour of stopping drug infusion, the infusion may be restarted at 50% of the original infusion rate (e.g., from 100 mL/hr to 50 mL/hr). Otherwise dosing will be held until symptoms resolve and the subject should be premedicated for the next scheduled dose.
 
Subjects who develop Grade 2 toxicity despite adequate premedication should be permanently discontinued from further trial treatment administration.
	
Subject may be premedicated 1.5h (± 30 minutes) prior to infusion of pembrolizumab with:
 
Diphenhydramine 50 mg PO (or equivalent dose of antihistamine)
 
Acetaminophen 500-1000 mg PO (or equivalent dose of analgesic)

Grades 3 or 4
 
Grade 3: Prolonged (i.e., not rapidly responsive to symptomatic medication and/or brief interruption of infusion); recurrence of symptoms following initial improvement; hospitalization indicated for other clinical sequelae (e.g., renal impairment, pulmonary infiltrates)
 
Grade 4: Life-threatening; pressor or ventilatory support indicated
	
Stop Infusion. Additional appropriate medical therapy may include but is not limited to:
 
 • Epinephrine** • IV fluids • Antihistamines • NSAIDs • Acetaminophen • Narcotics • Oxygen • Pressors • Corticosteroids • Epinephrine 
Increase monitoring of vital signs as medically indicated until the subject is deemed medically stable in the opinion of the investigator. Hospitalization may be indicated. **In cases of anaphylaxis, epinephrine should be used immediately.
 
Subject is permanently discontinued from further trial treatment administration.
	
No subsequent dosing


Appropriate resuscitation equipment should be available in the room and a physician readily available during the period of drug administration. For Further information, please refer to the Common Terminology Criteria for Adverse Events v4.0 (CTCAE) at http://ctep.cancer.gov IV=intravenous; NSAIDs= non-steroidal anti-inflammatory drugs; PO=oral administration
		

The treatment guidelines are intended to be applied when the Investigator determines the events to be related to pembrolizumab.

Note: If after the evaluation of the event, it is determined not to be related to pembrolizumab, the Investigator does not need to follow the treatment guidance. Refer to Section 5.2.1.2, [Table 3](#) for guidelines regarding dose modification and supportive care.

It may be necessary to perform additional procedures such as bronchoscopy, endoscopy, or skin photography as part of evaluation of the event.

5.6.1.1 Supportive Care Guidelines for Events of Clinical Interest and Immune-related Adverse Events (irAEs)

Immune-related Adverse Events (irAE)

Adverse events (both non-serious and serious) associated with drug exposure and consistent with an immune phenomenon may represent an immunologic etiology. These irAEs may be predicted based on the nature of the pembrolizumab compound, its mechanism of action, and reported experience with immunotherapies that have a similar mechanism of action. An irAE can occur shortly after the first dose or several months after the last dose of treatment and may affect more than one body system simultaneously. Particular attention should be paid to AEs that may be suggestive of potential irAEs as outlined in 7.2.3.2. Based on existing clinical trial data, most irAEs were reversible and could be managed with interruptions of pembrolizumab, administration of corticosteroids and/or other supportive care. For suspected irAEs, ensure adequate evaluation to confirm etiology or exclude other causes. Based on the severity of irAEs, withhold or permanently discontinue pembrolizumab and administer corticosteroids. Dose modification and toxicity management guidelines for irAEs associated with pembrolizumab are provided in Section 5.2.1.2, [Table 3](#).

Events of Clinical Interest (ECI)

Events of clinical interest (ECI) are non-serious and serious adverse events that may or may not be irAEs. ECIs must be reported to Merck **within 24 hours** regardless of attribution to study treatment. Information on how to identify and report ECIs can be referenced in Section 7.2.3.2.

